8.1.6 End-of-treatment visit (Visit 26)

All procedures and assessments listed in the flow chart in Section 2 for end-of-treatment should be performed and relevant data will be recorded in the eCRF.

Subjects must attend the end-of-treatment visit fasting according to the definition in Section 8.1.5.

The end-of-treatment form must be completed, final drug accountability performed and a completion session made in the IV/WRS. The case book must be signed.

8.1.7 Withdrawn subjects

If a subject is withdrawn from the trial, the investigator must aim to undertake procedures similar to those for Visit 26 as soon as possible. The subject should also have the follow-up contact performed, if possible. The subjects should be requested to return all used, partly used and unused trial product.

The end-of-trial form must be completed, and final drug accountability must be performed even if the subject is not able to come to the trial site. A withdrawal session must be made in the IV/WRS. The case book must be signed.

Although a subject is not obliged to give his/her reason(s) for withdrawing from a trial, the investigator must make a reasonable effort to ascertain the reason(s), while fully respecting the subject's rights. Where the reasons are obtained, the primary reason for not completing the trial must be specified on the end-of-trial form in the eCRF.

8.1.8 Follow-up period (Phone contact 27)

The investigator or delegated staff should call the subjects 30 days after Visit 26 has been conducted. Phone contact 27 (P27) will not be registered in IV/WRS.

The following information since Visit 26 will be reported by the subjects to the investigator via phone contact:

- Any AEs
- Any hypoglycaemia episode which occurs within 7 days after Visit 26
- Any changes in concomitant medications

8.2 Subject related information

8.2.1 Concomitant illness and medical history

A **concomitant illness** is any illness that is present at the start of the trial (i.e. at the screening visit) or found as a result of screening procedures. The disease under investigation (type 2 diabetes) is not considered as a concomitant illness and it is captured under diagnosis of diabetes.

Any change to a concomitant illness should be recorded during the trial. A clinically significant worsening of a concomitant illness must be reported as an AE.

Medical history is a medical event that the subject has experienced in the past. Only medical history considered relevant by the investigator should be reported.

The information collected for concomitant illness and medical history should include diagnosis, date of onset and date of resolution or continuation, as applicable.

8.2.2 Concomitant medication

A **concomitant medication** is any medication, other than the trial products, which is taken during the trial, including the screening and follow-up period.

Details of any concomitant medication must be recorded at the screening visit. Changes in concomitant medication must be recorded at each visit as they occur.

The information collected for each concomitant medication includes trade name or generic name, indication, start date and stop date or continuation.

If a change is due to an AE, then this must be reported according to Section [12](#). If the change influences the subject's eligibility to continue in the trial, the monitor must be informed.

8.2.3 Smoking status

Details of smoking status must be recorded at the screening visit. Smoking is defined as smoking at least one cigarette, cigar or pipe daily. The collected information should include whether or not the subject smokes or has smoked.

8.2.4 Demography

The following information has to be recorded, unless not permitted by local regulations:

- Date of birth
- Age
- Sex
- Race
- Ethnicity

8.2.5 Diagnosis of diabetes

The date of diagnosis of type 2 diabetes has to be recorded.

8.2.6 Diabetes complications

The following information has to be recorded:

- Diabetic retinopathy
- Diabetic neuropathy
- Diabetic nephropathy
- Macroangiopathy including peripheral vascular disease

8.2.7 Concomitant diabetes treatment

The following information has to be recorded:

- Current diabetes treatment (specify OD or BID basal insulin treatment)
- Total daily dose of current diabetes treatment
- Start date of current diabetes treatment
- Stop date of current diabetes treatment if applicable

8.3 Assessments for efficacy

The timing of the assessments and procedures are specified in the flow chart in Section [2](#).

8.3.1 Self-measured plasma glucose (SMPG)

At Visit 1, subjects will be provided with a blood glucose meter including lancets, plasma-calibrated test strips and control solutions as well as instructions for use. The subject will be instructed in how to use the device, and the instruction will be repeated as necessary during the trial.

The blood glucose meters use test strips calibrated to plasma values. Therefore, all measurements performed with capillary blood are automatically calibrated to plasma equivalent glucose values, which will be shown on the display.

Subjects should be instructed in how to record the results of the SMPGs in the diaries. The record of each SMPG should include date and value at each time point (before breakfast, 120 minutes after the start of breakfast, before lunch, 120 minutes after the start of lunch, before main evening meal, 120 minutes after the start of main evening meal, at bedtime) . All data from the diary must be transcribed into the eCRF during or following the contact. If obtained via phone and a discrepancy is later detected, the values in the eCRF should be corrected. If clarification of entries of discrepancies in the diary is needed, the subject must be questioned and a conclusion made in the subject's medical record. Care must be taken not to bias the subject.

8.3.1.1 Three times daily self-measured plasma glucose

Subjects will be instructed to perform the following SMPG measurements:

- Before breakfast
- Before lunch
- Before main evening meal

The three times daily SMPG will be performed on 3 random days in the week prior to a clinic visit/phone contact (Visit 3–Visit 26), according to the flow chart in Section [2](#). The plasma glucose value at each time point should be recorded in the diary.

8.3.1.2 7-point self-measured plasma glucose profiles

Subjects will be instructed to perform the following SMPG measurements:

- Before breakfast
- 120 minutes after the start of breakfast
- Before lunch
- 120 minutes after the start of lunch
- Before main evening meal
- 120 minutes after the start of main evening meal
- At bedtime

The 7-point SMPG profile should be performed on the day just prior to Visit 2, Visit 14 and Visit 26, according to the flow chart in Section 2. The plasma glucose value at each time point should be recorded in the diary.

Note that for Visit 14 and Visit 26, both three times daily SMPG and 7-point SMPG profiles are required. In the week prior to these visits, the measurements for both SMPGs may overlap. Since the 7-point SMPG profile includes the following:

- Before breakfast
- Before lunch
- Before main evening meal

these measurements can be used to replace one of the three times daily SMPG values required.

8.4 Assessments for safety

8.4.1 Hypoglycaemic episodes

Blood glucose should always be measured and recorded when a hypoglycaemic episode is suspected.

All plasma glucose values:

- ≤ 3.9 mmol/L (70 mg/dL) or
- > 3.9 mmol/L (70 mg/dL) when they occur in conjunction with hypoglycaemic symptoms

- should be recorded by the subject. These must be transcribed into the eCRF (hypoglycaemic episode form) throughout the trial from Visit 2 to the follow-up phone contact 27.

The record should include the following information:

- Date and time of hypoglycaemic episode
- The plasma glucose level before treating the episode (if available)
- Whether the episode was symptomatic
- Whether the subject was able to treat him/herself
- Date and time of last trial insulin and metformin administration prior to episode
- Dose of last trial insulin and metformin administration prior to episode
- Date and time of last main meal prior to episode. The definition for ‘main meal’ will be according to the investigator’s discretion.
 - Whether the episode occurred in relation to physical activity
 - Any sign of fever or other disease
 - Whether the subject was asleep when the episode occurred
 - If yes, whether the symptoms of the episode woke up the subject

The answer to the question: “Was subject able to treat him/herself?” must be answered “No” for an episode requiring assistance of another person to actively administer carbohydrate, glucagon, or take other corrective actions. Plasma glucose concentrations may not be available during an event, but neurological recovery following the return of plasma glucose to normal is considered sufficient evidence that the event was induced by a low plasma glucose concentration.

Oral carbohydrates should not be given if the subject is unconscious.

If the question “Was subject able to treat him/herself?” is answered “No”, the following information should be recorded:

- Who assisted in the treatment of the hypoglycaemic episode (i.e. family/friend/co-worker or similar, paramedic, doctor or other, please specify)
- Where the treatment was administered (i.e. at home/at friends/at work or similar, in an ambulance, emergency room/hospital or other, please specify)
- Type of treatment provided by other person (i.e. oral carbohydrates, glucagon, IV glucose or other, please specify)
- Were symptoms alleviated after administration of treatment?
- Factors contributing to the episode (i.e. physical activity, missed meal, diet changed, medication error (i.e. overdose, mix-up between products), miscalculation of insulin dose, other factors not listed, please specify or none)
- Did the subject experience seizure?
- Was the subject unconscious/comatose?
- Did the subject experience any of the following symptoms¹⁷?
 - Autonomic: sweating, trembling, hunger or palpitations
 - Neuroglycopenic: confusion, drowsiness, speech difficulty, visual disturbances, odd behaviour, impaired balance or incoordination

- General malaise: headache or malaise
 - Did the subject experience other symptoms? Please specify
 - Description of the episode, if applicable

A hypoglycaemic episode form must be filled in for each hypoglycaemic episode. If the hypoglycaemic episode fulfils the criteria for an SAE then an AE form and a safety information form must also be filled in, see Section [12](#).

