12.1 Definitions

Adverse event

An AE is any untoward medical occurrence in a subject administered a product, and which does not necessarily have a causal relationship with this treatment.

An AE can therefore be any unfavourable and unintended sign (including an abnormal laboratory finding), symptom or disease temporally associated with the use of a product, whether or not considered related to the product.

An AE includes:

- A clinically significant worsening of a concomitant illness.
- A clinical laboratory adverse event (CLAE): a clinical laboratory abnormality which is clinically significant, i.e. an abnormality that suggests a disease and/or organ toxicity and is of a severity that requires active management. Active management includes active treatment or further investigations, for example change of medicine dose or more frequent follow-up due to the abnormality.

The following should **not** be reported as AEs:

- Pre-existing conditions, including those found as a result of screening procedures (pre-existing conditions should be reported as medical history or concomitant illness).
- Pre-planned procedures unless the condition for which the procedure was planned has worsened from the first trial related activity after the subject has signed the informed consent.
- Non-serious hypoglycaemia is an AE, but is reported on a hypoglycaemic episode form instead of on an AE form, see Section [8.4.1](#).

The following three definitions are used when assessing an AE:

- **Severity**
 - **Mild** - no or transient symptoms, no interference with the subject's daily activities.
 - **Moderate** - marked symptoms, moderate interference with the subject's daily activities.
 - **Severe** - considerable interference with the subject's daily activities; unacceptable.

- **Causality**

Relationship between an AE and the relevant trial product(s):

- **Probable** - Good reason and sufficient documentation to assume a causal relationship.
- **Possible** - A causal relationship is conceivable and cannot be dismissed.
- **Unlikely** - The event is most likely related to aetiology other than the trial product.

- **Final outcome**
- **Recovered/resolved** - The subject has fully recovered, or by medical or surgical treatment the condition has returned to the level observed at the first trial-related activity after the subject signed the informed consent.

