Medical judgement must always be exercised, and when in doubt, the hospital contact should be regarded as a hospitalisation. Hospitalisations for administrative, trial related and social purposes do not constitute AEs and should therefore not be reported as AEs or SAEs. Hospital admissions for surgical procedures, planned before trial inclusion, are not considered AEs or SAEs.

- c A substantial disruption of a subject's ability to conduct normal life functions (e.g. following the event or clinical investigation the subject has significant, persistent or permanent change, impairment, damage or disruption in his/her body function or structure, physical activity and/or quality of life).
- d For example intensive treatment in an emergency room or at home of allergic bronchospasm, blood dyscrasias or convulsions that do not result in hospitalisation, or development of drug dependency or drug abuse.

Note: The seriousness criterion “important medical event” is not the same as the term “Medical event of special interest” (MESI).

Non-serious adverse event

A non-serious AE is any AE which does not fulfil the definition of an SAE.

Medical event of special interest

A medical event of special interest (MESI) is an event which, in the evaluation of safety, has a special focus. A MESI is an AE (SAE or non-serious AE) which fulfils one or more of the below defined MESI criteria.

Medication errors concerning trial products:

- Administration of wrong drug.
Note: Use of wrong DUN(s) is not considered a medication error unless it results in administration of wrong drug.
- Wrong route of administration, such as intramuscular instead of subcutaneous.
- Administration of an overdose with the intention to cause harm (e.g. suicide attempt).
- Accidental administration of a lower or higher dose than intended. That is a dose lower or higher than the intended dose; however the administered dose must deviate from the

intended dose to an extent where clinical consequences for the trial subject were likely to happen as judged by the investigator, although they did not necessarily occur.

Technical complaint

A technical complaint is any written, electronic, or oral communication that alleges product (medicine or device) defects. The technical complaint may be associated with an AE, but does not concern the AE itself.

Examples of technical complaints:

- The physical or chemical appearance of trial products (e.g. discoloration, particles or contamination)

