12.2 Reporting of adverse events

All events meeting the definition of an AE must be collected and reported. This includes events from the first trial-related activity after the subject has signed the informed consent until the end of the post-treatment follow-up period (i.e. Visit 1 to P 27). The events must be recorded in the applicable eCRF forms in a timely manner, see timelines below and [Figure 12-1](#).

During each contact with the trial site staff, the subject must be asked about AEs and technical complaints, for example by asking: “Have you experienced any problems since the last contact?”

All AEs, either observed by the investigator or subject, must be reported by the investigator and evaluated. Novo Nordisk assessment of expectedness is performed according to the following reference documents:

- Company core data sheet (CCDS) for NovoMix[®] 30, current version and any updates thereto

All AEs must be recorded by the investigator on an AE form. The investigator should report the diagnosis, if available. If no diagnosis is available, the investigator should record each sign and symptom as individual AEs using separate AE forms.

For SAEs, a safety information form must be completed in addition to the AE form. If several symptoms or diagnoses occur as part of the same clinical picture, one safety information form can be used to describe all the SAEs.

MESIs, regardless of seriousness, must be reported using both the AE form and the safety information form.

The AE form for a non-serious AE not fulfilling the MESI criteria should be signed when the event is resolved or at the end of the trial.

Timelines for initial reporting of AEs:

The investigator must complete the following forms in the eCRF within the specified timelines:

- **SAEs:** The AE form **within 24 hours** and the safety information form **within 5 calendar days** of the investigator's first knowledge of the SAE.

Both forms must be signed within 7 calendar days from the date the information was entered in the eCRF.

- **Non-serious AE fulfilling the MESI criteria:** The AE form, and safety information form **within 14 calendar days** of the investigator's first knowledge of the event.

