12.6 Precautions and/or overdose

Treatment with insulin may result in hypoglycaemia. A specific overdose for insulin cannot be defined. However, hypoglycaemia may develop over sequential stages if too high doses relative to the patient's requirement are administered. Symptoms may occur suddenly and include cold sweat, nervousness or tremor, anxious feelings, unusual tiredness, confusion, difficulty in concentrating, excessive hunger, temporary vision changes, headache, nausea and palpitation. Severe hypoglycaemia may lead to unconsciousness and even death.

Hypoglycaemia should be treated according to best available medical practice at the discretion of the investigator. Mild hypoglycaemic episodes can be treated by oral administration of glucose or sugary products. It is therefore recommended that the diabetic patient always carries sugar containing products. Severe hypoglycaemic episodes, where the patient has become unconscious, can be treated with glucagon (0.5 to 1 mg) given intramuscularly or subcutaneously, by a trained person, or with glucose given intravenously by a healthcare professional. Glucose must be given intravenously, if the patient does not respond to glucagon within 10 to 15 minutes. Upon regaining consciousness, administration of oral carbohydrates is recommended for the patient in order to prevent a relapse.

If hypoglycaemia is caused by an overdose, the event should be reported as a MESI.

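### Reporting instructions for non-serious hypoglycaemia caused by overdose contradict each other, and for self-treated episodes the form does not ask about a dosing error

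*Combined protocol and SAP*

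**What the plan says.** Four places in the protocol govern this event.

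- **Section 12.6** sets the rule for the cause: "If hypoglycaemia is caused by an overdose, the event should be reported as a MESI". It is not limited to severe or serious episodes.
- **Section 12.2** sets the forms: "MESIs, regardless of seriousness, must be reported using both the AE form and the safety information form". For a non-serious AE that is a MESI, both forms are due within 14 calendar days.
- **Section 12.1** says "A MESI is an AE (SAE or non-serious AE) which fulfils one or more of the below defined MESI criteria". The criteria listed are all medication errors, among them "Accidental administration of a lower or higher dose than intended", provided the investigator judges that clinical consequences were likely. The same section, in its list of things not to report as AEs, says: "Non-serious hypoglycaemia is an AE, but is reported on a hypoglycaemic episode form instead of on an AE form". No MESI exception is given there.
- **Section 8.4.1** adds the other two forms for SAEs: "If the hypoglycaemic episode fulfils the criteria for an SAE then an AE form and a safety information form must also be filled in". It points to Section 12 and does not mention MESIs.

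Section 8.4.1 also fixes the content of the episode form. The dosing-error item reads "Factors contributing to the episode (i.e. physical activity, missed meal, diet changed, medication error (i.e. overdose, mix-up between products), miscalculation of insulin dose". It sits in the block introduced by "If the question “Was subject able to treat him/herself?” is answered “No”, the following information should be recorded". The items recorded for every episode include the glucose value, the date, time and dose of the last trial insulin, the last main meal, physical activity, and fever or other disease. They do not include a dosing error.

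**The concern.** An investigator who learns of a non-serious low after a dosing error has two instructions for one event. The 12.1 bullet directs the site away from the AE form, and the 8.4.1 sentence, which staff are likely to consult when completing an episode form, asks for more only if the episode is an SAE. Sections 12.2 and 12.6 require the AE form and the safety information form. A site that relies on 8.4.1 and the 12.1 bullet would leave out a required safety report while believing it had complied.

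Medication errors are the only kind of MESI the protocol defines, and overdose hypoglycaemia is an obvious instance in an insulin trial. What is at stake is the completeness and timeliness of MESI reports reaching the sponsor's safety surveillance (Section 12.7.1). The efficacy analysis is not involved.

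**Working it through.** No arithmetic applies: the point depends on no rate, sample size or variance. The check compares the instructions by type of overdose-caused episode.

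| Episode | Dosing-error item asked? | Forms under 8.4.1 and the 12.1 bullet | Forms under 12.2 and 12.6 | Consistent? |
|---|---|---|---|---|
| Meets SAE criteria | Only if assisted | Episode, AE and safety information forms | AE and safety information forms | Yes |
| Assisted, not serious | Yes | Episode form | AE and safety information forms | No |
| Self-treated, not serious | No | Episode form | AE and safety information forms | No |

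**Routing.** The conflict depends on seriousness, not on whether the subject needed help. The direct contradiction is between the 12.1 bullet (episode form in place of the AE form) and 12.2 with 12.6 (AE form and safety information form for any MESI). The 8.4.1 sentence is an omission that points the same way as the bullet: it names SAEs and is silent on MESIs.

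**Prompt.** The self-treated row has a second gap. Section 12.6 itself says that no specific overdose can be defined for insulin, so calling an episode an overdose depends on what is known of its cause. For self-treated episodes the form does not ask. Other routes to that information exist, and each is partial:

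1. *Last dose against prescribed dose.* The last dose is recorded for every episode (8.4.1), and the prescribed dose is in the diary (8.4.7) and the eCRF (Appendix A, Section 4). A single oversized last injection would show as a mismatch. A repeated injection, an error in an earlier injection or a product mix-up need not, because routine dose recording covers only the three SMPG days and the first and last days of treatment (8.4.7, 8.6.2).
2. *AE enquiry at each contact (12.2).* The example wording is a general question about problems. A site that hears of a self-treated low in this way then meets the 12.1 bullet.
3. *Titration surveillance (14.2; Appendix A, Section 5).* Doses and episodes are reviewed centrally after each contact, but the stated purpose is to follow up deviations from the titration guideline.

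**Effect on analysis.** Every episode still gets an episode form, so the hypoglycaemia summaries and the negative binomial model in Section 17.4.1.2 keep their data. Neither Section 4.2 nor Section 17.4.1.2 contains a MESI endpoint or a MESI table.

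**The case against.** The strongest reply is that the protocol read as a whole already gives the answer. Section 12.6 is the specific rule for this event, 12.2 repeats the requirement regardless of seriousness, and 12.3 gives a 14-day limit when a previously reported non-serious AE later meets the MESI criteria. The 8.4.1 sentence says what to do if the episode is an SAE, not only if it is, and it refers to Section 12. The last dose is recorded for every episode, contact is at least weekly, and doses and episodes are reviewed centrally. The flow diagram for AE reporting (Figure 12–1) is not reproduced in the text available, so its routing cannot be checked.

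Much of this stands, and it rules out several stronger readings that a reader might infer:

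- *That self-treated overdose hypoglycaemia is not captured or has no route to a MESI report.* The documents do not support this: 12.2 and 12.6 require the report, and the episode and last dose are recorded.
- *That nearly all such events would be missed, for instance in proportion to the self-treated share of episodes.* That would need a severity split the documents do not give, and would assume that no one follows 12.2 or 12.6.
- *That the planned comparison of the arms is biased.* No MESI analysis is planned, and the documents give no figure showing that dosing errors differ between two and three daily injections.

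The reply does not remove the contradiction. The cross-reference in 8.4.1 is attached to the SAE case and leads to a section whose own bullet says the opposite of 12.2. Both rules are specific, one to non-serious hypoglycaemia and the other to overdose, and the text does not say which prevails.

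**Conclusion.** The point holds as a contradiction in reporting instructions together with a missing prompt. The contradiction covers all non-serious overdose-caused episodes, self-treated and assisted; the missing prompt affects self-treated ones. The expected consequence is some under-reporting of these events as MESIs, and inconsistent practice between sites. Its extent cannot be derived from the documents, because it depends on how often such errors occur and on which instruction sites follow. The conclusion assumes only that some sites will act on 8.4.1 and the 12.1 bullet as written. Hypoglycaemia counts, rates and models are untouched. The change is worth making because a required safety report is at issue and the correction is small.

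**What to change.** Reconcile Sections 8.4.1, 12.1, 12.2 and 12.6 with three edits:

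1. In 8.4.1, widen the trigger for the AE and safety information forms to an episode that fulfils the criteria for an SAE *or a MESI*.
2. In the 12.1 bullet on non-serious hypoglycaemia, add *unless it fulfils the MESI criteria*.
3. In 8.4.1, move the medication-error and dose-miscalculation item to the record completed for every episode.

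The first two edits resolve the contradiction; the third supplies the information needed to apply them to self-treated episodes. Figure 12–1 should be checked against the revised text. The cost is some wording, one more question on each episode form and some additional MESI forms. No treatment rule, endpoint or analysis changes.
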